### **Secondary Infant Outcomes**

The Infant CARE-Index (described above) also yields scores for the infant's contribution to the interaction. We included *infant difficultness*. Scores could range from 0 to 14. Higher scores reflect more infant difficult behaviors, such as crying and fussing, turning away, negative facial expressions, avoidance of eye contact, high arousal, and lack of engagement in a developmentally satisfying shared activity. Inter-rater correlations for difficultness on the 20% of videos selected for coding by an additional coder averaged  $r = .49$ .

At the final research visit, when infants were 12 months old, infant *externalizing* behavior, *internalizing* behavior, and *dysregulation* were measured with mother's report on the *Infant Toddler Social Emotional Assessment (ITSEA)* (Carter & Briggs-Gowan, 2006). The ITSEA was not included at the baseline or 6-month research visits because it is not valid for children younger than 12 months. The ITSEA has been standardized and normed on a nationally representative sample that was stratified to match the 2002 United States Census. Mothers rated their infant on an extensive list of behaviors from 0 (*not true/rarely*) to 2 (*very true/often*). T-scores were calculated for externalizing, internalizing, and dysregulation domains. In the study sample, alpha reliabilities for the domains were  $\alpha = .81$  for externalizing,  $\alpha = .68$  for internalizing, and  $\alpha = .80$  for dysregulation.

Cover Page
Statistical Analysis Plan

Official title of the study: Collaborative Perinatal Mental Health and Parenting Support in Primary Care

NCT Number: 02724774

Date of document: October 20, 2021 (created for ClinicalTrials.gov)

Analysis Plan

All analyses were conducted as intention-to-treat, analyzing all 252 cases as randomly assigned to the PFR and control group (CG). Multiple linear regression was used to examine the treatment effect of PFR (0 = CG, 1 = PFR) on study outcomes including the primary caregiver outcomes (parenting sensitivity, dyadic synchrony, understanding of infant and toddler behavior, and maternal confidence) and the secondary infant outcomes (infant difficultness, internalizing behavior, externalizing behavior, and dysregulation). Covariates included preferred language (0 = English, 1 = Spanish) and the baseline measure (unavailable for the ITSEA scales). Covariates were decided upon prior to analyzing outcome data to align with stratification in the randomization design (Moher et al., 2021) and obtain precise and unbiased estimates of the intervention effect (Van Breukelen, 2006). Adjusting for the baseline measure, which was expected to be the strongest correlate of outcomes, increases the precisions of intervention effect estimates. Standardized effect sizes (d) were calculated based on the unstandardized effect coefficient for PFR divided by the pooled standard deviation of the measure at baseline (if available) or at the follow-up time point (when the baseline measure was not available). The sign of the standardized effect was coded so that a positive d would reflect a desired positive effect of PFR on the given outcome (e.g., a positive d would reflect higher parent sensitivity or reduced externalizing behavior associated with PFR). We interpret ds as small (0.20), medium (0.50), and large (0.80; Cohen, 1988).

Regression analyses were conducted in Mplus Version 7.31 (Muthén & Muthén, 1998-2015). Covariate missingness was modeled to allow for inclusion of all 252 cases in all regression models, including cases with partially missing data (Muthén, et al., 2016; Muthén & Muthén, 1998-2015). Maximum likelihood parameter estimates with conventional standard

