## Research Plan and Methodology

### Study Design

This study was a randomized control trial. The effects of the intervention were tests using a two-arm randommixed controlled trial, comparing PFR (Arm 1) to Resource and Referral (Arm 2). Assessments were completed at T1 (before randomization), immediately after the intervention (T2), and a 6-month follow-up.

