Eligible mothers were identified via the Mental Health Integrated Tracking System (MHITS), the data base for MHIP managed by PHSKC in King County, or the PHSKC MSS database. Each MHIP participating community health center 'owns' the list of its patients and agreed for the county public health department to generate a monthly list of eligible pregnant women receiving mental health services at each clinic. The monthly list contained the names of their own eligible patients who were pregnant or had an infant less than three months of age. MHIP care managers and MSS social workers talked with women on the list by phone or at a clinic visit, briefly outlining the study. If the mother spoke, English or Spanish and interested in learning more about the study, the care manager or social worker connected her to the study recruitment coordinator either immediately or through a follow-up phone call. The recruitment coordinator conducted additional screening and answered any questions the mother had. If the mother was eligible and interested, the study research visitor scheduled and conducted the first research visit when the baby was between 6 and 12 weeks old. Written informed consent was obtained at the first research visit.

The project director initiated the randomization after the first research visit was completed. Randomization into the PFR intervention or control condition was computer generated, blocked on language group. Sample attrition was very low. Follow-up research visits were conducted when infants were 6 and 12 months old. At both follow-up timepoints, over 94% of families in both conditions completed the assessments. Overall, 95.2% completed all three research visits, 2.0% completed only the first visit, 1.6% completed the first and second visits, and 1.2% completed the first and third visits. Comparing the 240 cases with complete data with the 12 cases that missed one or both follow-up timepoints, attrition did not differ significantly by condition, nor did tests of condition-by-baseline characteristics reveal any evidence of differential attrition by condition with respect to language, race/ethnicity, age of mother, baseline mental health measures, or any of the primary outcome measures. At baseline, mothers with incomplete data were more likely to be separated, divorced or widowed, had lower incomes, and had more children.

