### ***Primary Caregiver Outcomes***

*Parenting sensitivity* was an observational measure collected at each research visit using the Nursing Child Assessment Teaching Scale (NCATS; Barnard, 1994). Mothers were presented with a list of activities and instructed to select the first activity that their infant could not yet do (e.g., hold onto a rattle, transfer an object from one hand to another, play pat-a-cake), to attempt to teach their infant. A standard set of manipulatives were provided for the activities. Teaching interactions were videotaped. Videotapes were scored by a blinded coder on 50 caregiver items measuring sensitivity to cues, response to distress, and fostering of social, emotional, cognitive growth, and contingency between caregiver and child. Items were scored yes (1) or no (0) and summed for a total sensitivity score. A single bilingual and bicultural coder, blind to intervention condition, was trained to reliability by a certified NCATS instructor and passed biannual reliability checks with a minimum of 85% inter-rater agreement with a master trainer.

The Infant CARE-Index (ICI, [name], 1979-2010) assesses parent-infant interaction during play and was included at each research visit. The mother was asked to play with her child as she usually would, and the interaction was filmed for 3-5 minutes. If mothers wanted to use toys, they were offered toys that they could use, or they could choose their own toys. The videos were scored by 16 coders certified to code the ICI for research purposes. To be certified, coders rated videos from a collection of videos gathered in multiple countries and that represented the full range of potential scores on the ICI constructs. Coders had to meet a standard for inter-rater reliability of  $r = .80$  on the measure of dyadic synchrony and an average of  $r = .70$  across all scales. Prior to coding the full sample in this study, coders coded 20 MBP study tapes, coder agreement was somewhat lower in this selection of videos ( $r = .74$ , range = .66 to .87). The coders' work was overseen by the author of the coding scheme ([name]). To address the study's primary hypotheses regarding caregiver outcomes, the rating for *dyadic synchrony* in play was used in the current study. Dyadic synchrony is any mutual pattern of behavior that

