enables the infant to explore the activity with interest and spontaneity and without inhibiting or exaggerating negative affect. Dyadic synchrony scores of 11-14 are sensitive, with mutual delight or a smooth, pleasing interaction. Scores between 7 and 10 are adequate, with satisfactory play but noticeable periods of desynchrony. Scores between 5 and 6 reflect clear, unresolved problems and limited playfulness, but no evidence of hostility or unresponsiveness. Scores between 0 and 4 reflect high risk, with a clear lack of empathy, insufficient or unsuccessful attempt to respond to the infant, or total failure to perceive or attempt to soothe the infant, and no play. As a further check of reliability, approximately 20% of the videos were randomly selected to be coded by a reliability coder. Inter-rater correlations for dyadic synchrony between the two coders averaged  $r = .67$ .

*Understanding of infant and toddler behavior* was measured by the Raising a Baby Scale (RAB; Kelly, Korfomacher, & Buehlman, 2008). The RAB is a measure of caregiver knowledge of infant and toddler social-emotional needs and developmentally appropriate expectations. At each research visit, mothers rated the 16 RAB items on a 4-point scale (*strongly agree* to *strongly disagree*;  $\alpha$  ranged from .68 to .71 across the three time points). The scale was summed, and higher scores indicate greater parental knowledge.

*Maternal confidence*, the perceptions mothers have of their ability to care for and understand their infants, was measured at each research visit using the *Maternal Confidence Questionnaire (MCQ)* (Zahr, 1991). Mothers rated 14 items on a 5-point scale (*never* to *always*;  $\alpha$  ranged from .66 to .76 across the three time points). Maternal confidence is reflected by the mean of the scale, with higher scores indicating greater confidence.

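### Four unranked primary outcomes, each measured at two follow-up visits, with no stated alpha, success rule or multiplicity control

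*SAP*

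**What the plan says.** The SAP (Analysis Plan) applies multiple linear regression, adjusted for language and the baseline value, to "the primary caregiver outcomes (parenting sensitivity, dyadic synchrony, understanding of infant and toddler behavior, and maternal confidence" and to four secondary infant outcomes. The four primary outcomes have no order, lead or composite. The Protocol (Primary Caregiver Outcomes) refers to the trial's "primary hypotheses regarding caregiver outcomes", in the plural, and does not say how they combine.

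The Protocol measures all four at every visit:

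- Parenting sensitivity "was an observational measure collected at each research visit".
- The Infant CARE-Index, which supplies dyadic synchrony, "assesses parent-infant interaction during play and was included at each research visit".
- For understanding of infant behavior: "At each research visit, mothers rated the 16 RAB items on a 4-point scale".
- For maternal confidence, the mother's perceived ability "to care for and understand their infants, was measured at each research visit".

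Under Participants, "Follow-up research visits were conducted when infants were 6 and 12 months old". Study Design gives the visits different roles: "Assessments were completed at T1 (before randomization), immediately after the intervention (T2), and a 6-month follow-up". Neither visit is called primary.

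For interpretation, the SAP labels standardized effects of 0.20, 0.50 and 0.80 as small, medium and large. It obtains ordinary maximum-likelihood standard errors. Neither document gives a significance level, a rule for declaring success, a joint test or a multiplicity adjustment, and neither says that the tests are unadjusted.

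**The concern.** With four equal primary outcomes and two follow-up visits, there are up to eight chances to find a significant primary result. The documents do not state how the visits were modelled. Separate regressions are plausible: the model is a linear regression with one baseline covariate, no repeated-measures model is described, and the Analysis Population Description refers to outcome-table numbers at both follow-ups. That reading gives eight primary comparisons. If only one visit is the target, there are four.

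What is at stake is how an isolated significant result is read. Without the number of comparisons and a statement that they are unadjusted, a reader cannot tell whether one p-value below 0.05 among the primary results is notable or close to what chance would produce.

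**Working it through.** The documents give no alpha, power or family-wise error figure, so there is nothing of the plan's own to reproduce.

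**Inputs from the documents.** Four primary outcomes (SAP, Analysis Plan); two follow-up visits (Protocol, Participants); 127 mothers assigned to PFR and 125 to control (Protocol, intervention and control sections). A positive standardized effect means benefit (SAP), so false benefit is counted in one direction.

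**Assumptions, not in the documents.** Two-sided 5% per test, hence 2.5% in the benefit direction; a separate regression per visit; any one significant result counts as benefit; no true effect on any outcome; normal test statistics with the correlations shown.

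**Independent tests.** P(at least one false benefit) = 1 - (1 - 0.025)^k.

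- k = 1: 2.5%
- k = 4: 1 - 0.975^4 = 9.6%
- k = 8: 1 - 0.975^8 = 18.3%

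**Correlated tests, eight comparisons.** The correlation between two test statistics is the between-outcome value times the between-visit value, where each applies. The result is P(any z > 1.96), from 2,000,000 simulated draws per cell:

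| Between outcomes | Between visits 0.3 | 0.5 | 0.7 |
|---|---|---|---|
| 0 | 17.7% | 17.0% | 15.7% |
| 0.3 | 16.0% | 15.3% | 14.0% |
| 0.5 | 14.3% | 13.5% | 12.5% |
| 0.7 | 12.0% | 11.4% | 10.4% |

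The moderate cells (0.3-0.5 between outcomes, 0.5-0.7 between visits) give 12.5-15.3%. Counting either direction, the table's corner cells give 33.0% (0/0.3) and 20.9% (0.7/0.7), against 5% for one test.

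The upper limit of 0.7 is a rough choice. The Protocol's reliabilities (knowledge scale alpha .68-.71, confidence scale .66-.76, dyadic synchrony inter-rater r .67) imply ceilings on raw-score correlations such as sqrt(.71 x .76) = 0.73 between outcomes and sqrt(.68 x .71) = 0.69 between visits. They bound baseline-adjusted test statistics only loosely. The table's minimum is therefore not a floor: 0.7/0.9 gives 8.9% and 0.9/0.95 gives 5.9%.

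**Four comparisons (one visit).** At between-outcome correlations of 0, 0.3, 0.5 and 0.7: 9.6%, 8.8%, 7.8% and 6.5%.

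**With Holm.** When no effect is real, a false claim requires the smallest p-value to pass the first step.

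- Eight tests: 0.05/8 = 0.00625 two-sided. If independent, false benefit is 1 - (1 - 0.003125)^8 = 2.5%. It is 1.4-2.4% as the correlations run from 0/0.3 to 0.7/0.9.
- Four tests within a visit: 0.05/4 = 0.0125 two-sided, so at most 4 x 0.00625 = 2.5% for that visit, and at most 2 x 2.5% = 5% across both visits.

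**Power cost.** Assume a baseline-outcome correlation of 0.5. The standard error in SD units is sqrt(1 - 0.5^2) x sqrt(1/127 + 1/125) = 0.866 x 0.1260 = 0.1091. The effect detectable with 80% power at 5% is (1.960 + 0.842) x 0.1091 = 0.306 SD. For one true effect of that size (expected z = 2.80), power at the first Holm step is:

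- four tests, critical z 2.498: Phi(2.80 - 2.498) = 62%
- eight tests, critical z 2.734: Phi(2.80 - 2.734) = 53%

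**The case against.** The strongest reply is that the error rates belong to a decision rule the documents do not contain. The plan's only interpretive scale is one of effect size. The four outcomes are distinct constructs: observed teaching, observed play, knowledge and confidence. The Protocol speaks of hypotheses in the plural, and the secondary outcomes are already kept apart. If each outcome supports only its own claim, the need for adjustment is debatable.

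Much of this stands. A reader might infer that the plan lets any single significant result count as benefit, or that the trial's false-positive rate is 18%. The documents support neither: they state no such rule, no alpha, no per-visit modelling and no single family. For the same reason eight tests should not be imposed as the only family, since that would itself be a choice made after the fact.

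The reply does not remove the gap. A size label for an effect is not error control. The plan does not say that the outcomes are to be read as separate claims or that their p-values are unadjusted. On either view the reader needs the number of primary comparisons and their unadjusted status.

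It may also be said that the time for this has passed, since the SAP is dated October 2021 and describes completed analyses. That limits the remedy to disclosure and clearly labelled additional results; it does not make them unnecessary.

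**Conclusion.** The concern holds in a conditional form and should be fixed. It is established from the text that four unranked primary outcomes were each measured at two follow-ups, with no alpha, primary visit, success rule or multiplicity control described. As written, the plan yields unadjusted tests of several equal primary outcomes.

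The size is conditional. Under the any-one-significant reading, the chance of a false benefit is about 4 to 7 times that of one test over eight comparisons (10.4/2.5 = 4.2; 18.3/2.5 = 7.3), or about 3 to 4 times over four (6.5/2.5 = 2.6; 9.6/2.5 = 3.8). These ratios rest on the assumed level, modelling and correlations. The direction does not depend on the correlation chosen: even at 0.9/0.95 the eight-comparison rate is more than twice 2.5%.

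**What to change.** State the alpha, the number of primary comparisons, how the two visits were modelled, and that the stated analyses carry no multiplicity adjustment.

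Beside the unadjusted estimates and confidence intervals, report Holm-adjusted p-values for all eight primary comparisons and also for the four within each visit. Showing both avoids imposing one family. The within-visit version controls error for each visit, not across the two. Label both as added after the analyses.

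Describe any primary result that is significant only before adjustment as not controlled for multiplicity, and do not rest an overall claim of benefit on it alone. Do not choose a lead outcome or primary visit now.

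The cost is a few lines of analysis and wording, with no new data: Holm needs only the existing p-values, and the unadjusted results stay in view. The price is that some results with raw p < 0.05 will not survive. For a single true effect of 0.31 SD, with 252 cases and an assumed baseline correlation of 0.5, power at the first Holm step falls from 80% to about 62% over four tests or about 53% over eight.
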